Data management will be responsible for monitoring interviews completed, which will be done monthly. The interviewers will be sent a list of interviews that have not yet been completed with study participants. This process differs from query letters which request information on specific data items within a form.

Data management will periodically conduct an audit program. A random subset of cases will be selected from the files. In this way, problems with data collection and transmission can be detected early. In addition, data will be monitored for secular trends in data completeness and quality. Study audits will be conducted several times over the course of the study.

Only the study generated ID will used for any and all references to records for purposes of cleaning and overall quality.

***Ame00068213

We added the University of Michigan IRB to the language about the HIPAA waiver for recruitment and language about the HIPAA authorization for enrolled participants recruited from the Detroit Medical Center.

Study Statistical Design

Sample Size Determination:

The primary outcomes of interest in the randomized trial are ED visits and hospitalizations, both overall and heart related. In a sample of 443 patients at a 12 month follow-up, there were significant differences between those that received "take PRIDE" and those that did not in hospitalizations overall (difference of 0.26 times hospitalized) and heart related hospitalizations (difference of 0.41 times hospitalized) and also in overall ED visits (difference of 0.17 visits). The secondary outcome of interest is cardiac symptom experience: number, frequency, and bothersomeness. Several cardiac symptoms will be summed to obtain overall scores: chest pain, shortness of breath, waking with chest pain, waking with shortness of breath, and palpitations. In a sample of 460 patients randomized to the intervention or usual care, researchers found that the change in the number and frequency of symptoms differed significantly between the intervention and comparison group (difference of 0.36 and 1.16 in scores, respectively).

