To detect a 0.15 difference in the change in the number of overall ED visits between the intervention and comparison groups at a 12 month follow-up, a sample size of 188 will be necessary in the intervention and comparison groups for a total sample size of 376 at the end of 12 months. This number will be sufficient to detect a 0.20 difference in hospitalizations and will also be sufficient to detect differences in cardiac symptoms. In a recent iteration of the intervention, the recruitment response rate was 48% and the loss to follow-up was about 20%. Therefore, 1300 subjects will be contacted for participation and 376 subjects will be enrolled.

Analysis of patient outcomes:

Descriptive statistics will be computed for all outcomes overall and stratified by randomized study arms. Health care utilization: Outcome variables including hospitalizations and ED visits will first be assessed as dichotomous variables and will be analyzed using chi-square analyses followed by logistic regression modeling. Because these are count variables, Poisson regression analyses will also be conducted. Cardiac symptoms: The presence of cardiac symptoms will be assessed individually using chi square tests and logistic regression modeling. The cardiac symptoms will also be summed to obtain an overall score of symptoms as well as a score for the frequency and severity. These will be continuous and will be analyzed using analysis of covariance (ANCOVA) and multiple linear-regression modeling assuming normal distributions. If necessary, transformation will be used to ensure normality or Poisson regression will be used if Poisson distributions are found for these variables. They may also be recoded as categorical or ordinal variables and analyzed using chi-square tests and multiple or cumulative logistic regressions.

Functional health status: Functional health status will be assessed using the PROMIS Global Health Scale and/or PROMIS-29. The scores are continuous variables and will be analyzed similarly to the symptoms using ANCOVA and linear regression modeling where the normality assumption is appropriate. They may also be re-coded as categorical or ordinal variables and analyzed using chi-square tests and logistic regressions.

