Intervention dose received: The dose of the intervention will be examined using the logs completed by the health educator. The subject will receive one point for each of 4 sessions attended and a point for each of the three components completed: goal setting, tracking form, and the judgment/reaction. The scores will only be available for the intervention group and will describe average level of participation within the intervention group using frequencies and mean scores.

The components of the intervention: Observation, judgment, goal setting strategies, outcome expectancy and efficacy can also be described individually. Participants in the intervention group may be stratified based on the dose score and outcomes compared using t-tests or chi-square tests of homogeneity to describe impact of dose on outcomes. Instrumental variable approaches to estimating the complier-average causal effect of the intervention will be applied, with compliance defined using two different choices of cut-off on the performance score.

Change over time: The focus of the mixed-model (for continuous outcomes) and GEE (for discrete outcomes) analyses will be to assess changes in dependent measures over time, and whether these changes differ between program participants and "usual care" controls. The effect of time as well as the interaction between time and program participation (program vs. waitlist control) will be included as factors in all models.

Generalizability of the intervention: To determine how effective the intervention would be if duplicated in a similar population, it will be important to examine non-consenters to see if those who choose to participate have certain factors that may be correlated with improved outcomes not present in those who do not participate. Aggregate data from the DMC including demographics, and health care use values will be obtained on those patients that meet the criteria for participation but were not enrolled in the randomized controlled trial to be compared to enrolled participants using t-tests and chi-square tests to discover any differences.

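### With 376 enrolled and about 20% lost, about 150 per arm finish, so the stated detectable differences of 0.15 (ED visits) and 0.20 (hospitalizations) are not delivered

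*Combined protocol and SAP*

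**What the plan says.** All references are to the combined protocol and SAP.

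- **Sample Size Determination, target and number.** The target is worded as follows: "To detect a 0.15 difference in the change in the number of overall ED visits between the intervention and comparison groups". The number per arm is then given: "a sample size of 188 will be necessary in the intervention and comparison groups". The total is tied to the 12-month time point: "for a total sample size of 376 at the end of 12 months". For the other primary outcome: "This number will be sufficient to detect a 0.20 difference in hospitalizations". The word change is attached to ED visits only.
- **Sample Size Determination, attrition.** An earlier use of the intervention had a 48% recruitment response and about 20% loss to follow-up. The paragraph then concludes that 1300 people will be contacted and 376 enrolled. The recruitment section on electronic medical records also gives 376 as the baseline number.
- **Sample Size Determination, prior evidence.** In 443 patients at 12 months, the difference in overall hospitalizations was 0.26. The other differences were in "heart related hospitalizations (difference of 0.41 times hospitalized) and also in overall ED visits (difference of 0.17 visits"). No event rates or standard deviations are given.
- **Analysis of patient outcomes.** The two utilization outcomes "will first be assessed as dichotomous variables and will be analyzed using chi-square analyses followed by logistic regression modeling". A further step is added: "Because these are count variables, Poisson regression analyses will also be conducted".
- **Change over time.** GEE is planned for discrete outcomes, and every model is to carry a time-by-program term: "The effect of time as well as the interaction between time and program participation (program vs. waitlist control) will be included as factors in all".

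Alpha, sidedness, power, standard deviation, event rates and within-person correlation are not stated.

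**The concern.** The same number, 376, is both the required count at 12 months and the count enrolled, although the paragraph itself expects a fifth to be lost. The detectable differences therefore describe a trial with more completers than this one will have.

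The figures also look optimistic in a second way. A difference in change between two yearly counts is noisier than a difference in 12-month counts, because the variation of both years enters. With no rate or variance stated, it is fair to ask what event rates would make 188 per arm enough, and whether the prior-trial differences are compatible with such rates.

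ED visits and hospitalizations are the primary outcomes. A reader who accepts 376 as adequate for 0.15 and 0.20 could take a null result as evidence against effects of that size when the trial had less power than claimed.

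**Working it through.** **Inputs from the plan.** 188 per arm; d = 0.15 (ED) and 0.20 (hospitalizations); 376 enrolled; about 20% loss; prior differences 0.17, 0.26 and 0.41. **Assumed, because not stated:** two-sided 5% and 80% power, z-values 1.960 + 0.842 = 2.802.

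**1. The plan's figure.** 188 cannot be reproduced from what is given. Solving backwards, SD = d × √(188/2) / 2.802, which gives 0.519 for ED visits and 0.692 for hospitalizations.

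**2. Attrition (needs no variance).** Completers: 376 × 0.80 = 300.8, or 150.4 per arm. For fixed SD, alpha and power, the detectable difference scales with 1/√n, so the factor is √(188/150.4) = 1.118.
- ED: 0.15 × 1.118 = 0.168.
- Hospitalizations: 0.20 × 1.118 = 0.224. This holds only if 188 was just sufficient for 0.20; the plan says sufficient, so there may have been slack.
- Power at the stated differences: Φ(2.802 × √0.80 − 1.960) = Φ(0.546) = 71%. If 90% power had been intended: Φ(3.242 × √0.80 − 1.960) = 83%.

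**3. Event rates at which 188 per arm gives 80% power.** Let L be the comparison-arm yearly rate, with Poisson counts and a flat rate in that arm. Setting n·d²/2.802² equal to the summed per-person variance of the two arms gives:
- 12-month counts: variance sum 2L − d.
- Raw change, stable rate per person: variance sum 4L − d (two years in each arm).
- Log-link time-by-program interaction: variance (3/L + 1/(L − d))/n, effect ln[L/(L − d)].

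| Highest L for 80% power | ED, d = 0.15 | Hospitalizations, d = 0.20 |
|---|---|---|
| Raw change, 188 per arm | 0.172 | 0.290 |
| Log-link interaction, 188 | 0.236 | 0.379 |
| 12-month counts, 188 | 0.344 | 0.579 |
| 12-month counts, 150 | 0.29 | 0.48 |

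Example: 188 × 0.15² / 2.802² = 0.539, so L = (0.539 + 0.15)/4 = 0.172 for raw change and (0.539 + 0.15)/2 = 0.344 for 12-month counts.

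**4. Comparison with the prior figures.** If a prior difference is a per-patient mean difference with equal baselines, the comparison rate cannot be lower than that difference.
- ED: floor 0.17. At L = 0.17, raw-change power is Φ(0.15/√(0.53/188) − 1.960) = 81%. It falls to 72% at L = 0.20 and 52% at 0.30 (log-link: 89% and 64%). The last two rates are illustrations, not figures from the plan.
- Hospitalizations: heart-related admissions are part of all admissions, so the floor would be 0.41. At L = 0.41, raw-change power is Φ(0.20/√(1.44/188) − 1.960) = 63%, and log-link power is 75%. With 150.4 per arm these become 53% and 66%. On 12-month counts, power at 0.41 is 94% with 188 and 88% with 150.

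**The case against.** The case against a stronger claim is good, and most of it stands. A reader might infer that 188 per arm fails under the plan's Poisson analysis unless event rates are lower than the prior trial allows. The documents do not support that.

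- **ED visits.** The only prior figure, 0.17, lies below every limit for 188 per arm (0.172, 0.236, 0.344). On raw change the room is tiny, and a 0.15 effect at a rate of 0.17 would leave 0.02 visits a year. That is implausible but not a contradiction.
- **12-month counts.** Both limits (0.34 and 0.58) exceed the floors of 0.17 and 0.41, so on that scale the prior figures do not contradict the claims for 188 per arm.
- **Hospitalizations.** The 0.20 sentence does not mention change; that scale comes from the later commitment to a time-by-program term. The 0.41 floor is an inference, and it sits oddly beside an overall difference of only 0.26. With 0.26 as the floor, raw-change power is 85% at 188 per arm.
- **Correlation.** If the counts keep Poisson variance but correlate at about 0.34 or more within a person, 80% power returns at L = 0.41. Correlation that comes only from stable differences between patients does not help raw change: it adds equally to the variances and the covariance and cancels.
- **Error rates.** Alpha and power are assumed here, so no stated calculation has been shown to be miscomputed.

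On attrition, it could be said that 376 enrolled is a slip for 376 completers. But the recruitment section repeats 376 at baseline, and 376/1300 = 28.9% fits its 25–30% expected agreement. It could also be said that medical-record extraction at the Detroit Medical Center would recover utilization for some people lost to interview. That covers only consenting participants from that source, and the main-study data sources list only telephone surveys and educator logs. If half the loss were recovered (90% retained), the differences would be 0.158 and 0.211 and power about 76%.

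**Conclusion.** The point holds in two parts of different strength.

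**Firm.** By the plan's own numbers, about 150 per arm reach 12 months, not 188. The ED difference that can be detected rises from 0.15 to about 0.17, which is the whole effect seen in the prior trial. The hospitalization figure rises from 0.20 to about 0.22 if 188 was only just enough. This rests on the 20% loss applying to the utilization outcomes and on no particular variance or error rate. The 71% power figure additionally assumes a design for 80% power at two-sided 5%.

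**Conditional.** If change is the analysis scale, 188 per arm has little margin for ED visits and appears short for hospitalizations: about 63–75% power, or 53–66% with 150 per arm. This requires Poisson counts with no help from within-person correlation, and the prior 0.41 being a per-patient mean difference with equal baselines. If 12-month counts are compared without overdispersion, whether there is a shortfall depends on rates the documents do not give.

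The inference that the prior figures rule out the stated ED power, or that the planned Poisson analysis cannot work at this size, goes further than the documents allow.

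**What to change.** Keep enrolment at 376 and rewrite the detectable differences in Sample Size Determination.

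1. Base them on the expected completers, about 150 per arm, and make the number enrolled and the number at 12 months agree with the 20% loss.
2. Say which scale each utilization outcome is powered on, 12-month count or change, and use the analysis that will be applied to it.
3. State the alpha, power, comparison rate and variance assumed.
4. Replace the statement that the number suffices for a 0.20 difference in hospitalizations with the recalculated value.

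The cost is a reworded section and less favourable stated figures. No patients, visits or procedures are added.

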Study Title: A Partnership to Translate an Evidence-based Intervention (Take Heart) for Vulnerable Older Adults with Heart Disease

NCT02950818

3/21/2019

This document discusses methodologies for both the pilot study and the portion of the main study that will be conducted with participants recruited through the Detroit Area Agency on Aging, other community sources, the UM Institute of Gerontology database, or the UMClinicalStudies.org website. We have indicated which information applies to the pilot study, the main study or both.

ROLES/RESPONSIBILITIES OF STUDY PARTNERS:

Focus groups, Pilot and Main Study

The UM Center for Managing Chronic Disease (CMCD) is responsible for contacting, screening and enrolling participants (based on lists of names of interested individuals provided by DAAA or who call the project hotline directly after seeing flyers or other advertisements). CMCD is responsible for survey data collection, data storage and management, and analysis. CMCD will train the DAAA-affiliated health educators to deliver the intervention and will provide oversight and technical assistance. CMCD is also responsible for all reporting to funder and for managing subcontracts.

The Detroit Area Agency on Aging (DAAA) will be responsible for delivering the intervention to participants, under direction from the Center for Managing Chronic Disease. They will also be responsible for scheduling participants into sessions, and collecting attendance and other process data, such as topics covered in intervention sessions. They will also engage in some limited recruitment activities (e.g., posting flyers). NOTE: These activities will be overseen by the UM IRB, as DAAA does not have their own IRB.

The Detroit Medical Center (Rosa Parks Geriatric Center) will be responsible for the following: Identifying potential participants based on specific ICD-10 codes from electronic medical records, and sending these lists securely to CMCD. They are also responsible for extracting health care utilization data at two time points (baseline and 12 months) from electronic medical records of participants who provide consent for this. Finally, if deemed convenient for participants by the Community Working Group (an advisory group for the project), DMC may host some intervention sessions (led by DAAA staff) on site at their medical campus.

Recruitment Flowchart

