[name] from the DMC will collaborate with the DMC IT team to conduct regular data pulls from the electronic medical record of patients meeting the inclusion criteria, with the understanding that this study has an approved waiver of informed consent from the Wayne State University and University of Michigan IRBs. No sensitive medical information, other than the fact that the patient meets the specific study criteria and contact information, will be accessed. DMC physician Fellows will proceed to further review medical records results from ICD-10 pulls to determine likely study participant eligibility, and will be trained to look for exclusion criteria and indicators that patient would not benefit from program. Secondary review by a DMC Fellow and the DMC Data Coordinator, if needed, will further ensure eligibility before sending lists of prospective participants to CMCD. DMC staff will upload a password-protected MS Excel file to M+Box for access by UM/CMCD project director. CMCD will store patient data within the password-protected RedCap database.

Eligible patients will be mailed a recruitment package that includes a personalized cover letter from the study's principal investigators indicating collaboration with their physician as part of DMC, an information sheet describing the study and decline postcard. All recruitment packages and telephone contacts will originate from the CMCD project office to ensure patients are provided with accurate and consistent contact information about the study. The use of a recruitment script, including brief screening items, during telephone contact ensures that all potential participants receive standardized information regarding the study.

Based on previous studies involving participants from similar demographic and socioeconomic groups, we anticipate that 25-30% of those invited to take part in the study will agree to participate. Recognizing that the population of patients targeted for enrollment in the proposed research will be, on average, managing various significant psychosocial challenges and comorbidities, a conservative enrollment figure of 30% is anticipated for purposes of planning. The estimated number of patients available within the DMC is adequate to reach the figure required by our sample size determination (n=376 at baseline).

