Throughout recruitment calls, each patient will be encouraged to ask questions and told that they are free to withdraw from the study at any time, for any reason. A toll-free [contact]) will be provided so that potential participants can call the research office with additional questions at any time.

Randomization will be stratified by four categories of a risk score based on data from prior studies that includes age, gender, and number of comorbidities, using responses from the baseline interview. To reduce the predictability and resulting bias due to block randomization, random block sizes (e.g., lengths of 8, 10, 12 subjects) will be used and blinded to investigators. Prior to recruitment, a permuted block randomization schedule will be created using the RANTBL and RANUNI functions in SAS to generate blocks with varying sizes of 8, 10, or 12 and random numbers for group assignment within each of the 4 categories of risk score.

Once enrolled, participants recruited through the Detroit Medical Center (DMC), will be asked to complete another consent document that includes a HIPAA Authorization statement. This will authorize DMC to release specific health information related to Take Heart after the recruitment phase (first, middle and last name, street address, city, state, zip code, email address, home and cell phone number, primary care provider and specialist, number of visits to the emergency department and hospitalizations during the year prior to the Take Heart study and the year of your participation in the study), to the University of Michigan School of Public Health research staff.

WHAT HAPPENS TO SUBJECTS DURING RESEARCH:

Focus groups:

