Participant debrief: Participants will be asked the following questions regarding their satisfaction with various program topics and elements, in a group format or, if preferred by participants, oneon-one: What did you like about this element/activity/topic? What could we do to make it better? They will also be asked: Is there anything else that should be in the program that is not? How well do you feel like the program addressed your needs? What can we do to keep participants' interest in the program? Did you use the materials—why/why not and how?

Note that this data is for purposes of program refinement.

Pilot-Test Baseline Survey: We will pilot-test our baseline survey to see what areas, if any, of the survey need adjustment before we begin the RCT. We will also ask up to 10 participants who agree to pilot the survey to answer check-in questions about their experience with the survey every 2-3 pages. This will allow us to gather more detailed information about what areas of the survey can be improved. We have uploaded the feedback questions we plan to ask in Section 29.

From the audio recordings we will transcribe participant answers to the feedback questions; and record information about length of the survey and participant engagement with interviewer. An alpha-numeric participant ID will be used in all transcribed materials to protect the individuals' identity.

Note that this data is for purposes of survey refinement.

Main Study

Data sources for this study include: (1) participant telephone surveys at two time points: baseline and 12 months; and (2) health educator logs indicating sessions attended and participation in intervention activities (copy uploaded to Section 44).

Telephone surveys: These will be conducted by trained research assistants, and will collect health, psychosocial, and demographic data. The vast majority of measures used in this study are standard measures that have been used in previous studies. A copy of the survey is uploaded in Section 29. A copy of our Interviewing Protocol, which includes a description of interviewer training and oversight, is uploaded in Section 44. Telephone surveys will be audio recorded for quality assurance.

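### The sample size text uses 376 both as the number needed at 12 months and as the number enrolled, although it cites about 20% loss to follow-up

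*Combined protocol and SAP*

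**What the plan says.** Three statements bear on the point.

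- **Study Statistical Design, Sample Size Determination, requirement.** To detect a difference of 0.15 in the change in overall ED visits, 188 per arm are needed, "for a total sample size of 376 at the end of 12 months". On hospitalizations it adds: "This number will be sufficient to detect a 0.20 difference in hospitalizations".
- **Same paragraph, enrolment.** It reports that in a recent iteration "the recruitment response rate was 48% and the loss to follow-up was about 20" per cent, and draws the conclusion: "Therefore, 1300 subjects will be contacted for participation and 376 subjects will be enrolled".
- **Recruitment from electronic medical records at the Detroit Medical Center.** The available patients are said to be enough for the "sample size determination (n=376 at baseline").

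Neither alpha, sidedness, power nor an SD is stated anywhere.

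Two further places concern where 12-month outcomes come from. Under Roles/Responsibilities of Study Partners, the medical center's tasks include "extracting health care utilization data at two time points (baseline and 12 months) from electronic medical records of participants who provide consent for this". The HIPAA authorization paragraph, which applies to participants recruited through that center, covers the "number of visits to the emergency department and hospitalizations during the year prior to the Take Heart study" and during the study year. By contrast, Data Collection, Main Study, lists only telephone surveys "at two time points: baseline and 12 months" and the health educator logs.

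**The concern.** A number required at 12 months and a number enrolled can be equal only if nobody is lost. The paragraph itself cites about 20% loss between stating the two. Two explanations are possible:

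- **Reading A (literal).** 376 is the evaluable number, and the loss was cited but never applied.
- **Reading B.** 376 already includes the loss, and the statement that it refers to 12 months is wrong.

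Overall ED visits are a primary outcome and the one that sets the sample size. Under A, the 0.15 target rests on a number the trial should not expect to have at 12 months. Under B, the target stands but the plan misstates its requirement. A reader cannot tell which applies.

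**Working it through.** **Inputs.** From Sample Size Determination: 188 per arm; 376 total at 12 months; 376 enrolled; loss about 20%; target differences 0.15 (ED visits) and 0.20 (hospitalizations); differences in the earlier trial 0.17 (overall ED visits) and 0.26 (overall hospitalizations); response rate 48%; 1300 contacted. From the medical center recruitment text: 376 at baseline; expected uptake 25–30%. Alpha and power are my assumptions: two-sided 5%, with power of 80% or 90%.

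**1. The plan's own figures.** 2 × 188 = 376, so the total reproduces. The 188 itself cannot be reproduced without alpha, power and SD.

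**2. Enrolment needed for 376 at 12 months.** N/(1 − d) = 376/0.80 = 470. The common shortcut of multiplying by 1.2 gives 452 (226 per arm). Neither is 376; only d = 0 returns 376.

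**3. Expected 12-month interviews from 376 enrolled.** 376 × 0.80 = 300.8, about 301 (188 × 0.80 = 150.4 per arm), a shortfall of 75. At 15% loss the figure is about 320; at 25% it is 282.

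**4. Could 376 already include the loss?** 150/0.80 = 187.5, rounded up to 188 per arm, so B is arithmetically possible. It is not independent evidence, because 188 × 0.80 is about 150 whatever the origin of 188. The plan never states 150.

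**5. Consequence under A.** At unchanged power the detectable difference scales with √(376/N). Power at 0.15 is Φ[(1.96 + z_power) × √(N/376) − 1.96]. The middle row assumes, for illustration, that medical records recover half of the 75 lost.

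| Evaluable N | Detectable ED difference | Power at 0.15 if planned at 80% | If planned at 90% |
|---|---|---|---|
| 376 | 0.150 | 80% | 90% |
| 338 | 0.158 | 76% | 87% |
| 301 | 0.168 | 71% | 83% |

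For hospitalizations, 0.20 × √(376/301) = 0.224. This is an upper bound, because the plan says only that the number suffices for 0.20.

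**6. SD of change implied by 0.15.** SD = 0.15 × √(n/2)/(1.96 + z_power).

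| | 80% power | 90% power |
|---|---|---|
| A, n = 188 per arm | 0.52 | 0.45 |
| B, n = 150 per arm | 0.46 | 0.40 |

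The SD and power actually used would therefore settle which reading is right.

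**7. Does the contact figure help?** 376/1300 = 28.9%, which fits the 25–30% uptake with no allowance for loss. The 48% response rate would give 1300 × 0.48 = 624. Neither calculation shows the 20% being used.

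**The case against.** **Reading B has support in the text.** Two places put 376 at enrolment or baseline and one phrase puts it at 12 months, and the enrolment conclusion follows directly on the loss rate as if the rate had been used. That makes B plausible. It does not remove the error, because under B the statement about 12 months is false.

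**Losing an interview is not the same as losing a primary outcome.** ED visits and hospitalizations are to be extracted from medical records, and the data-source list that omits records may simply not have been updated. This stands in part. However, extraction depends on consent, the authorization is described only for participants recruited through the medical center, and the main study also recruits in the community. Nowhere is it said that records replace missing interviews. The possible evaluable number therefore runs from 301 to 376.

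**The 20% is another study's experience.** True, so 301 is an expectation and not a fixed figure. It is nevertheless the only loss rate the plan offers, and the plan draws its enrolment figure from that sentence.

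**The effect is modest.** Also true: 0.168 is still just under the 0.17 of the earlier trial, and 0.224 is below its 0.26. For ED visits, though, almost no margin remains.

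**The power figures are illustrative.** They use a normal approximation for a difference in mean change, while the planned analyses are chi-square, logistic, Poisson and GEE. The contradiction does not depend on them.

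**Conclusion.** The concern holds. The plan gives 376 as the number at 12 months and as the number enrolled, cites about 20% loss, and nowhere reconciles the three. If that loss applies here, 376 enrolled gives about 301 12-month interviews, about 150 per arm, under either reading.

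The consequence depends on the reading. Under A, the detectable ED-visit difference is about 0.168 instead of 0.15 at unchanged power, or power at 0.15 falls by roughly 7 to 9 percentage points (90% to 83%, or 80% to 71%, on the assumptions above). Record-based outcomes could offset some of this. Under B, 0.15 is unaffected and only the time point is wrong.

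Confidence is high for the contradiction and lower for the power figures. Correcting 376 alone would not make the precision of the primary outcome checkable; alpha, power and SD are needed as well.

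**What to change.** In Sample Size Determination, state separately the number enrolled and the number expected to be evaluable at 12 months, and give the alpha, sidedness, power and SD used. Then, according to what was actually calculated:

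- **If 376 was the evaluable requirement:** write, for example, *A total of 376 will be enrolled; with about 20% loss, about 301 are expected to have 12-month interviews.* Restate the detectable ED-visit difference (about 0.168) or the power for about 301, and recompute the hospitalization difference from its own SD.
- **If 376 already allowed for loss:** move 376 from the end of 12 months to enrolment, state about 150 per arm at 12 months, and keep 0.15.

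Make the medical center recruitment text agree. State whether record-based ED visits and hospitalizations count toward the evaluable number, and bring the main-study list of data sources into line.

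The cost is wording only, using inputs the sponsor should already hold, provided about 301 is accepted in the first case. Keeping 376 at 12 months would instead correspond to enrolling 470; that figure is given for reference and is not a request.

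As a separate, minor matter, state the single uptake rate behind the 1300 contacts, since 48% and 28.9% cannot both be its basis.
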